### **3.0 Study Procedures**

#### **3.1 Study Design**

In this multi-site study, participants may be enrolled at PVAMC, RIH, and UAB. UAB will also receive referrals from BVAMC. This study aims to enroll 264 participants across the sites: 88 with PNES, 88 with PTE, and 88 with TBI without PNES or PTE. To meet recruitment goals, we will enroll both Veterans and civilians participants. Civilians will be seen at Rhode Island Hospital. All participants will be imaged at 2 time points and will complete self-reports, assessments and symptom measures as detailed in this protocol. The PNES and PTE participants will receive 12 sessions of CBT-Sz.

#### **3.2 Recruitment Methods**

Referrals to the study will come from the VA hospital systems for Veteran participants, and civilian participants will be referred from clinicians in the respective catchment areas. We plan to use multiple recruitment strategies to reach potential participants. In order for the findings to be applicable to Veterans and civilians with seizures, referrals from both cohorts will be accepted. All recruitment documents and language for recruitment documents will be reviewed and approved by each site's appropriate IRB prior to release. As required, outside press releases, advertisements and media postings, Facebook, Twitter and Craigslist.com will go through the appropriate site's Public Affairs Officer. We will also register the study on [clinicaltrials.gov](https://www.clinicaltrials.gov) and will post study info the American Epilepsy Society (AES) studies list ([https://www.aesnet.org/research/clinical\\_research/clinical\\_trials\\_site](https://www.aesnet.org/research/clinical_research/clinical_trials_site)).

Physicians, rehabilitation, mental health, nursing and other professionals as appropriate at the associated site's VA's and hospitals, CBOCs and the Veteran Centers will be educated about this study. They will be asked to share information about this study with potential participants. If their patient is interested in hearing more about the study, the clinician will give them a copy of the IRB approved study brochure so the patient can contact the study staff directly. The clinician will also have the option to ask the potential participant if they would like their name to be shared with the study PI, so study staff can contact them. If the potential participant agrees for their name to be shared, the professional will document this in their record and provide the participant's contact information to the PI or his designated research staff through the study site's approved method (i.e. encrypted email, calling the research staff directly on their site associated phone extension, medical record referral process as available). After the referral names are received, the research staff will send the potential participant a letter. The letter will state which provider shared their name and the fact that they were interested in hearing more about the study. The letter will include information about when the research staff would be calling them.

We will also advertise using IRB approved language through brochures, fliers or PowerPoint advertisement posted throughout the sites, the CBOCs, Veteran Centers and in other community locations and events likely to be visited by Veterans and their families. We will issue

press-releases to the site's local news outlets and may submit to online posting sites, such as Craig's List, each site's Research Service website, and their Twitter and Facebook accounts

We may also advertise through Veteran Associated Newsletters and magazines and local newspapers as well as through staff wide email sent through the public relations or the director's office as locally approved and available. We will also use our medical record with a waiver for screening prior to enrollment to identify potential participants and send them an IRB approved letter telling them about the study and informing them of a date when research staff will call them to see if they are interested.

See the addendum for the study recruitment language, brochures, fliers and PowerPoint ads.

### **3.3 Informed Consent Procedures**

Prior to conducting of any of the study procedures, eligible potential participants will be required to provide informed written consent. Potential participants that are deemed eligible on pre-screen and are interested in the study will be asked to come to the PVAMC main building or building 32 in a room as assigned for review of the consent form and HIPAA before any study procedures are performed. The PI or study staff will review the consent form with the potential participant and assure understanding of the study involvement. Participants will be given adequate time to review and comprehend all study activities, and ask questions prior to being asked if they agree to participate. If they agree, then they will sign the consent form. If needed participants may be asked to sign releases of information to gather additional clinical information from their health care providers for this study.

Participants will be told that they may refuse participation without any negative consequences, and if they decide to participate, they will be free to withdraw from the study at any time. They will be reminded that their decision to enroll in this study will not affect their relationship with their healthcare providers or the care they receive now or in the future at the PVAMC.

### **3.4 Inclusion/Exclusion Criteria**

#### Inclusion criteria for PNES, ES and TBI (w/o PNES or ES) participants

- Individuals with history of documented TBI (any severity)
- Males and Females ages 18-60 years
- Women of child bearing potential, if currently using appropriate contraception

#### Inclusion criteria of PNES and ES participants

- Diagnosed by video/EEG with lone PNES or by EEG with lone ES
- Patients must have at least 1 PNES or 1 ES during the year prior to enrollment.

#### Exclusion Criteria of PNES, ES and TBI (w/o PNES or ES) participants

- Current or past year self-injurious behavior
- Current suicidal intent (BDI suicide question 9 score of >1)
- Current or past year psychosis
- Pending litigation or current application for long term disability

- Active substance or alcohol use disorders (dependence), at the discretion of the investigator if they preclude participation in the study
- Serious illness requiring systemic treatment or hospitalization; the participant either completes therapy or is clinically stable on therapy, for at least 30 days prior to study entry
- Inability to fill out the self-report surveys
- Women who are or/are attempting to become pregnant during the study
- Ineligible or unwilling to complete MRI imaging
- Inability to document TBI

#### Exclusion Criteria for PNES and ES participants

- Inability or unwillingness to participate in CBT and assigned homework
- Currently enrolled in cognitive therapy aimed at PNES (Current CBT or other psychotherapy may be administered)
- Concurrent mixed ES/PNES or equivocal video/EEG findings in discerning between ES and PNES will not be enrolled.

### **3.5 Diagnosis and Study Enrollment Procedures**

The diagnosis of lone PNES or lone PTE, and TBI without PNES or PTE will be clinically established prior to study enrollment. All pre-screening, prior to consent, of potential participants will be done with an IRB-approved waiver or signed release of information.

### **3.6 Study intervention behavioral challenge (CBT-Sz)**

CBT-Sz will be given to 176 participants (88 with PNES; 88 with ES) by a trained therapist in 12 individual weekly one-hour sessions (the first CBT-Sz session is called the Introduction session, followed by 11 more sessions). Study sessions will be administered according to the manualized protocol. Participants will have weekly homework to complete between the sessions that may take up to 1 hour to complete. Missed CBT-Sz sessions will be made up, if possible, during the same week of the scheduled appointment or by scheduling the session the following week. If that is not possible, the session is counted as a missed appointment of the 12 sessions. The CBT-Sz therapist will document the missed sessions and report them to the research coordinator. Clinical experience suggests that the more appointments attended by the participant, the more response to the intervention. Participants will continue CBT-Sz sessions regardless of the number of missed sessions.

Participants who are unable to attend the CBT-Sz office appointments due to transportation limitations can have sessions over the telephone. The feasibility and safety of the tele-CBT has been demonstrated in our CBT-PNES trial and other CBT trials. Initial sessions, if possible, will take place in-person to establish patient-therapist rapport, and to provide the patient with the treatment packet (forms, modules, mailing envelopes, etc.) that will be used, if needed, in any future telephone sessions. If not, materials will be provided to participants at the baseline or 1st MRI visit. Tele-CBT follows the format and duration of face-to-face sessions and can be completed by any trained IRB approved study therapist at either the Providence VAMC, Rhode Island Hospital, and University of Alabama, Birmingham. Therapy sessions will be digitally recorded to ensure therapy adherence and competence.

### **3.7 Study Evaluations**

**Clinical Evaluations:** The Schedule of Evaluations in Table below includes all clinical study evaluations for the PTE and PNES participants. TBI participants will also complete the study

evaluations at baseline, endpoint, and Month 8 and 12. A mark in a cell indicates that a particular evaluation is to be performed at a particular study visit.

	Pre-Screening	Entry	Baseline After consent day 0 up to day 14	Every week (beginning Day 14 from consent). Introduction plus Session 1 through Session 11 (exit)	Interval Assessments Sessions- 6, ("Midpoint") 10 ("Endpoint")	Month 8 and 12
Informed Consent		RS				
MRI Safety		RS			RS, prior to 2 nd MRI	
EEG Report Diagnosis Validation	X	N *				
Neurological Exam	X	N*				
SCID-5-RV (Axis I)			RS			
SCID-5-PD (Axis II)			RS			
TLEQ (Trauma history)			P			
MRI			RS will coordinate		RS will coordinate At least 13 weeks after first MRI and within the 2 weeks after the last session	
Cognitive Bhvrl Th (CBT-Sz)				Psy		
Seizure Calendar Review (log)			For the month retrospective before consent	RS		
MoCA (v8.1 and v8.2)			RS or Psy		RS or Psy	
Adverse Events /Side Efx			P		P	
Med review			RS	RS		
Adherence Assessments				RS	RS	
CGI-S/I (Global impress.)			RS		RS	
GAF / OHS (Function/disability)			RS		RS	
LIFE-RIFT (Work/social function)			RS		RS	
BDI-II (Depression)			P	P	P	P
BAI (Anxiety)			P		P	P
PCL-5 (PTSD sxs, severity)			P		P	
FAD (family functioning)			P		P	
MFS (Modified Fear Survey)			P		P	
BIS-11 (Impulsivity)						
SCL-90 (Gen sxs severity)			P		P	

QOLIE-31 (quality of life)			P		P	
NSI (TBI symptoms)			P		P	
ESTXFU						RS

**Legend** - X –referring physician, N- Neurologist, P-Participant, RS- Research Staff, Psy-Psychiatrist or Psychologist.

**Neurological Examination:** which documents a complete history, medical and neurological examination based on NINDS Common Data Elements (CDE), will be documented from chart extraction.

\* If neurological examination was not performed within 36 months prior to enrollment into the study, it will be obtained by the study neurologist after consent is obtained. This routine exam will take about 30 minutes and will include mental health, medical, family, social and developmental history and will be assessed during the baseline period.

**Symptom Surveys:** Self-report questionnaires assessing psychiatric symptoms, family functioning and social functioning will be administered during baseline (within the 2 weeks after consent and validation of diagnosis) prior to the initiation of the CBT-Sz intervention, as well as at Session 6 (called “midpoint”) and Session 10 (called “endpoint”). “Endpoint” surveys are collected at Session 10 rather than at the final session to maximize data collection. To monitor depressive signs and symptoms, the Beck Depression Inventory self-report will be given at each session. Seizure calendars will be reviewed at each session. The participant self-reports will take approximately 45 to 75 minutes to complete. The SCIDs can take up to 180 minutes. After the sessions end, the participants will have two follow-up interviews at months 8 and 12 from the first CBT-Sz session to assess functional status, symptoms and seizures. These follow-up assessments will take about 30 minutes.

**Assessment of seizure frequency via seizure calendar:** Participants will confirm they have had at least 1 seizure in the past year. Baseline seizures will be documented retrospectively for the 1 month prior to enrollment on the seizure calendar (referred to as “seizure log”); The participant will then fill out one seizure log per week, prospectively. Participants will be trained to complete the log so seizures are correctly and consistently logged. Participants can ask family members to assist in supplementing information for completion of calendars. The clinician will review the calendar with the participant to confirm documentation. Research staff will review the seizure calendar with the participant to assure it is complete and nothing has been left out, in order to validate the reported numbers.

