**Participants with TBI without PNES or PTE will complete/have:**

- The consent process (giving written permission to take part in the study)
- MRI Safety screening
- Diagnosis validation
- Baseline and endpoint measures at the time of fMRI's (the same as Seizure participants)
- Two MRI brain scan approximately 13 weeks apart
- Follow-up at 8 and 12 months from the first fMRI with the TBI follow up survey (TBITXFU) (this assessment will ask about symptom frequency and treatments and will be conducted by research staff either in person or via phone call).

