**Allowable windows:**

Research staff will aim for participants to meet the desired timeline, unexpected events occur in people's lives, therefore, for this study the researchers will allow for up to a 3 day window on either side of the desired timeline for completion of the study procedures and assessments before identifying them as a deviation. The CBT-Sz sessions may also be completed in up to 16 weeks.

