#### The fMRI stress task:

The fMRI task elicits mild-to-moderate level of stress similar to the level of stress experienced in everyday situations.

For both fMRIs, the stress tasks consists of a control math task (CMT) designed to be non-stressful and a stress math task (SMT) intended to induce a moderate amount of psychosocial stress. The SMT is based on the Trier Social Stress Task and the Montreal Imaging Stress Task. All participants perform the CMT followed by the SMT. All instructions (during practice and fMRI) are scripted to assure uniformity of the experimental conditions. CMT includes subtraction problems in which participants have to select the correct answer from two choices by pushing the corresponding button on the response box. Throughout the task, participants hear different pre-recorded messages that provide positive evaluative feedback regardless of actual performance. After completing the CMT and prior to SMT initiation, participants are told that “researchers” will be evaluating their performance and will give them feedback during the task, that for each question they have a variable time of 1-5 seconds to respond in order for their answer to count, and for their data to be used and to be reimbursed the full compensation of \$100, they needed to achieve an unspecified number of correct answers based on the average score for people of their age and level of education (i.e., deception is used to induce mild-to- moderate stress response). During the SMT, Participants perform more difficult subtraction problems than the CMT with three answers to choose from. Participants also hear different pre-recorded messages, all of which provide negative evaluative feedback regardless of actual performance (mild-to- moderate psychosocial stress). Both tasks also include instances of a tone condition where participants are instructed to press “1” or “2” on the response box while hearing a train of tones. The tone condition was designed to monitor attentiveness during the task regardless of actual performance. At the end of the imaging session each participant will be debriefed and informed that they earned the maximum amount of reimbursement irrespective of their performance.

This stress task target the emotion processing (limbic) circuits, including medial-frontal and medial- temporal regions.

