### **4.3 Withdrawal of Participants**

Protocols are established to address and contain any high risk aspects of the proposed works, including increase in seizures or depressive symptoms. If during the study participants are found to develop medical or mental health problems, they will be referred for appropriate treatment, as indicated in the safety protocol. If clinically indicated, he/she will be withdrawn from the study. If a participant develops nonepileptic psychogenic status (NEPS) or status epilepticus, the participant will be referred to the local emergency department for observation, and if clinically indicated, will be withdrawn from the study.

Participants who decide that they do not want to start or finish the CBT-Sz sessions will be asked to continue completing self-reports and assessments and the second fMRI, in order to compare completers with any non-completers.

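### In the CBT-Sz groups the last scheduled adverse event ask is at Session 10, before the second stress-task scan, and none is marked after that scan or at Months 8 and 12

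*Combined protocol and SAP*

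**What the plan says.** Section 3.7 states that its table holds all clinical evaluations for the PTE and PNES participants, and adds: "A mark in a cell indicates that a particular evaluation is to be performed at a particular study visit". The row "Adverse Events /Side Efx" carries a P (completed by the participant) under Baseline and under the interval column for Sessions 6 and 10. Its weekly cell and its Month 8 and 12 cell are empty.

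In the same interval column the second MRI has its own timing note: "At least 13 weeks after first MRI and within the 2 weeks after the last session". The AE row has no such note. On the endpoint assessments, Symptom Surveys (section 3.7) says that "surveys are collected at Session 10 rather than at the final session to maximize data collection". It does not name the AE form.

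The stress task is run at both scans and relies on deception and negative feedback. Under The fMRI stress task: "At the end of the imaging session each participant will be debriefed".

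TBI controls give baseline and endpoint measures when they are scanned, described as "the same as Seizure participants".

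On safety in general, the Safety Monitoring Plan undertakes to record every AE during the study, and section 5.0 undertakes ongoing assessment. Potential Risks to Participation names distress from the MRI task and a temporary rise in symptoms from the sessions. Section 4.3 says: "Protocols are established to address and contain any high risk aspects of the proposed works, including increase in seizures or depressive symptoms".

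**The concern.** The general text promises complete AE collection but states neither when nor how participants are asked. The schedule is the only place in the available text that turns the promise into visits, and it stops at Session 10. What follows Session 10 includes the second exposure to a task designed to induce stress, in participants whose condition the Background attributes to trauma and stress (PNES), and then follow-up to Month 12.

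The PI, the IRBs and the DMC can act only on events that are recorded. After Session 10, an injury, an emergency visit or an anxiety reaction that the participant does not volunteer has no scheduled question to bring it out. The follow-up questionnaire for the seizure groups is described as covering seizure frequency and treatments.

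**Working it through.** **Inputs**
- Sessions: Introduction plus 11, so 12 (section 3.6).
- Marked AE asks in the CBT-Sz groups: Baseline, Session 6, Session 10 (section 3.7 table).
- First scan: in the 2 weeks before the first session. Second scan: at least 13 weeks after the first and no more than 2 weeks after the last session (Neuroimaging assessment).
- Missed sessions: made up in the same or the following week, otherwise counted as missed (section 3.6).
- Follow-up: Months 8 and 12 from the first session (Symptom Surveys).
- Group sizes: 88 PNES, 88 PTE, 88 controls (section 3.1).

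**Second scan, on schedule.** Put the Introduction at week 0 and Session k at week k. Session 10 is then week 10 and Session 11 is week 11. The scan must fall by week 11 + 2 = 13. If the first scan was at week -2, the 13-week minimum allows weeks 11 to 13. If it was at week 0, only week 13 fits. The gap from the last marked ask is 11 - 10 = 1 to 13 - 10 = 3 weeks.

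**With a make-up.** If Session 11 moves to week 12, the scan is due by week 14, a gap of 14 - 10 = 4 weeks, plus the 3-day window.

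**Follow-up.** One month is 365.25 / 12 / 7 = 4.35 weeks.
- Month 8 = 34.8 weeks, which is 34.8 - 10 = 24.8 weeks after Session 10.
- Month 12 = 52.2 weeks, which is 52.2 - 10 = 42.2 weeks after Session 10.
- From the second scan to Month 8: 34.8 - 13 = 21.8 to 34.8 - 11 = 23.8 weeks.

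**Before Session 10.** Of the 12 sessions, 12 - 2 = 10 have no AE mark. However, no recall window is stated, so the Session 6 and Session 10 asks may look back over the whole interval since the previous one. BDI-II, the seizure calendar and medication review are marked weekly.

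**Months 8 and 12.** BDI-II, BAI and the follow-up interview are scheduled, so symptoms and seizures are reviewed. The AE row is not marked.

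**Controls.** They have no midpoint assessment. Their endpoint measures come at the second scan, but whether before or after the tasks is not stated. Months 8 and 12 carry no AE mark for them either.

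**The case against.** The strongest reply is that a blank cell proves little. The reading rule says what a mark means, and the BIS-11 row is entirely blank although section 3.7 lists that scale as administered. The AE row records a participant form, not the whole AE process, and the details may sit in Addendum F or the safety appendix, neither of which was available. The risks named in section 4.3 are already followed weekly by BDI-II and the seizure log, and every scan ends with a debrief. The phrase "the same as Seizure participants" could also mean that seizure participants give endpoint measures at the scan.

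Much of this stands. It limits the point to scheduled asks in the available text. It does not remove the point: the table claims to be complete for these groups, the MRI row needed its own timing note while the AE row has none, and Symptom Surveys places the endpoint at Session 10. If the AE mark was meant to cover the scan, the table should say so.

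A reader might infer three stronger things, which the documents do not support:
- *That AEs go uncollected, or that the plan contradicts itself.* Scheduled forms can coexist with continuous reporting.
- *That most weeks of therapy go unasked about.* Ten sessions lack a mark, but with no stated recall window the Session 6 and 10 asks may cover them.
- *That the gap before the second scan could reach 8 weeks*, because "The CBT-Sz sessions may also be completed in up to 16 weeks". That needs Session 10 on time and Session 11 at week 16. The make-up rule in section 3.6 would have Session 11 held by week 12 or counted as missed. About 4 weeks is the supportable figure.

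**Conclusion.** The point holds as a low-cost safety improvement. As marked, CBT-Sz participants have no AE ask after Session 10. That leaves the second stress scan (1 to 3 weeks later, about 4 with a make-up) and Months 8 and 12 (about 25 and 42 weeks later) without one. The gap before Session 10 is small.

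This rests on reading blank AE cells as no scheduled ask, on weekly sessions, and on Addendum F and the safety appendix not already providing these asks. The number of AEs missed cannot be estimated. No aim, hypothesis or planned analysis is affected. The groups are not randomized, so even equal asking would not turn a comparison of seizure groups with controls into a measure of tolerability.

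**What to change.** 1. Mark the AE row after the tasks at the second scan, using the existing debrief, and at Months 8 and 12, in all groups.
2. Print 'since the last AE ask' as the recall window at every ask, including Sessions 6 and 10. A short fixed window would leave a hole: 30 days (4.3 weeks) before Month 8 reaches back only to week 34.8 - 4.3 = 30.5, leaving 30.5 - 13 = 17.5 weeks after a week-13 scan unasked.
3. Report AEs and SAEs descriptively by group, without tests.
4. If Addendum F or the safety appendix already sets these asks, cite it in the table and align the AE row.

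**Cost.** Three added asks per CBT-Sz participant: 3 x 176 = 528. Controls add 2 x 88 = 176 if their endpoint ask is simply placed after the tasks, or 3 x 88 = 264 if the post-scan ask is new. The total is 704 to 792. At an assumed 3 minutes each this is 704 x 3 / 60 = 35 to 792 x 3 / 60 = 40 staff hours. Over 2 to 5 minutes the range is 704 x 2 / 60 = 23 to 792 x 5 / 60 = 66 hours. There are no new visits or participants.

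**Downsides.** The recorded AE count will rise somewhat. A scan-day ask catches only immediate distress, and delayed effects of the second scan would wait for a Month 8 recall of about 22 to 24 weeks unless volunteered. A weekly AE ask is optional.
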